7.5. Lost to Follow-Up

A participant will be considered lost to follow-up if he or she fails to return for the EOS assessments within the permitted EOS visit window and is unable to be contacted by the study site staff.

The site should make every effort to regain contact with the participant and reschedule the missed visit as quickly as possible. These contact attempts should be documented in the participant's medical record or study file. Participants lost to follow-up will not be replaced.

7.6. Participant Replacement

Participants will not be replaced.

8. STUDY ASSESSMENTS AND PROCEDURES

Please refer to Section 1.3, Table 1-1 and Table 1-2 for the schedule of assessments. It may be necessary to perform these assessments at unscheduled timepoints if deemed clinically necessary by the Investigator.

8.1. Screening Procedure

Once a participant has signed the ICF (see Section 11.1.1), an identification number will be assigned to him/her and the study related screening procedures will start. The screening period will last up to 28 days before the start of the treatment (C1D1).

Protocol waivers or exemptions are not allowed.

A participant will be randomized into the study after he/she has signed the ICF, all eligibility criteria have been met and the IMRT plan has been sent to the RT-QA Review Center (see Section 11.2.2). The IMRT plan must be approved by the RT-QA Review Center prior to the start of the IMRT.

The central laboratory assessments needed for participant eligibility are specified in Table 8-2. Local laboratory results only for HBV/HCV/HIV tests (obtained within 2 weeks before ICF signature) and HPV status (also see Section 8.1.2) may be accepted if report is available. If the previous central laboratory results are older than 7 days, the hematologic, renal and hepatic laboratory assessments should be rechecked by a local laboratory before the first dose administration.

No participant replacement will be allowed. All randomized participants will be included in the Intent-to-treat (ITT) population.

8.1.1. Baseline Disease Characteristics and Assessments

Baseline participant and disease characteristics will be assessed during the 28-day screening period.

The following should be performed prior to randomization to confirm eligibility and disease staging: demographics, vital signs, physical examination, weight, height, ECOG performance status (ECOG PS), ECG, nutritional status, dental examination, audiometry, coagulogram, laboratory tests (see Section 8.3.7 for further details), ¹⁸F-FDG-PET, i.v. contrast-enhanced CT-scan or MRI of head and neck, CT-scan of chest, and fiberoptic endoscopy.

Medical history includes tobacco and alcohol consumption history and habits.

Tumor staging should be established using the AJCC/TNM Staging System, 8th Ed., based on radiological imaging. Please refer to Section 8.2.1 for further details on radiological imaging.

If several ECGs (scheduled and unscheduled) are performed during the screening, the most recent results should be recorded in the eCRF.

¹⁸F-FDG-PET, i.v. contrast-enhanced CT-scan or MRI of head and neck, and CT-scan of chest are only accepted if they are performed within 4 weeks before randomization. Dental examination, audiometry, HBV/HCV/HIV tests, and fiberoptic endoscopy performed within 2 weeks before ICF signature do not have to be repeated during screening.

Results from the central laboratory should be used for defining participant eligibility during screening, except for:

- HBV/HCV/HIV tests that may be performed by a local laboratory within 2 weeks before ICF signature (see Section 8.3.7).
- HPV status by p16 IHC that may be obtained locally (see Section 8.1.2).

8.1.2. HPV Status in Participants with OPC

In participants with OPC, primary tumors must be HPV-negative, determined by p16 IHC.

p16 cutoff for determination of HPV status is defined as following: For HPV status of OPC participants, p16 expression by IHC is scored as positive if a total H-Score \geq 210 or \geq 70% of the tumor cells with 3+ staining intensity in nucleus and cytoplasm. H-Score should be calculated by the formula: H = [% weak (1+)x1] + [% moderate (2+)x2] + [% strong (3+)x3].

Results obtained prior to the participant's consent to participation in the study are acceptable, provided a report is available. If no report is available for HPV status by p16 IHC, the assessment can be done locally on an archived tumor sample.

If the site is not able to perform HPV testing by p16 IHC, it will be evaluated by a central pathology laboratory designated by the Sponsor. In this case, randomization into the study can only occur after confirmation of HPV-negative status has been communicated to the site.

The results of existing local data must be captured on the appropriate eCRF upon enrolment into the study after the participant has signed the ICF.

8.1.3. Highly Effective Contraceptive Measures and Pregnancy Test

To be enrolled in the study women of childbearing potential and men with female partners of childbearing potential must agree to use highly effective contraceptive measure(s) from ICF signature to 6 months after completing chemotherapy treatment or 3 months after last dose of xevinapant/matched placebo, whichever is the latest (see inclusion criteria 11 in Section 5).

Non-sterilized males who are sexually active with a female partner of childbearing potential must agree to use condom and spermicide from ICF signature to 6 months after last administration of chemotherapy or 3 months after last dose of xevinapant/matched placebo, whichever is the latest (see inclusion criteria 11 in Section 5). Because male condom and spermicide is not a highly effective contraception method it is strongly recommended that female partners of male study participants use highly effective contraceptive method(s) throughout this period.

Contraceptive measures which are considered highly effective comprise combined (estrogen and progestogen containing) hormonal contraception associated with inhibition of ovulation (oral, intravaginal, transdermal), progestogen-only hormonal contraception associated with inhibition of ovulation (oral, injectable, implantable), intrauterine device, intrauterine hormone-releasing system, bilateral tubal occlusion, vasectomized partner and sexual abstinence.

If a hormonal contraception is chosen, the use of a barrier method (preferably male condom) is mandatory due to potential risk of CYP3A4/5 induction by xevinapant that may reduce hormonal contraception efficacy.

Abstinence is acceptable only if it is consistent with the preferred and usual lifestyle of the participant. Periodic abstinence (e.g., calendar, ovulation, symptothermal, or postovulation methods) and withdrawal are not acceptable methods of birth control.

Females without childbearing potential, defined as those who are surgically sterile (i.e., bilateral tubal ligation, bilateral oophorectomy, or complete hysterectomy) or those who are post-menopausal (defined as 12 months with no menses without an alternative medical cause) and have a follicle-stimulating hormone level in the laboratory normal range for post-menopausal phase at screening, do not need a pregnancy test.

Serum pregnancy test (β -HCG) will be conducted during screening by a central laboratory in women of childbearing potential (see Table 8-2). On C1D1, negative serum pregnancy status should be rechecked locally by serum or urine test only if the previous central laboratory result is older than 7 days. After C1D1, serum or urine tests should be performed locally according to schedule presented in Table 1-1 and Table 1-2

Should a pregnancy still occur, all study treatments should be discontinued immediately.

The Sponsor should be notified of any pregnancy that occurs in female participants or partners of male participants during participation in studies with xevinapant by submitting a specific pregnancy form. Any reports of pregnancy in participants or partners of participants will be followed up as described in Section 9.4.2.

8.2. Efficacy Assessments

Assessment of tumor response to treatment will be assessed locally and centrally according to the Response Evaluation Criteria in Solid Tumors (RECIST v1.1) but will also take into consideration clinical, anatomopathological, and functional assessments of the tumor, as described in Appendix 13.5.

Tumor assessment and HRQL questionnaires or assessments should be continued until disease progression (as per RECIST v1.1) occurs or Month 60 post-randomization, whichever occurs first.

Participants who progress (as per RECIST v1.1) will enter the OS follow-up period at the time of the event and will be followed up for survival status at least every 3 months, until the EOS (see Section 7.2).

In case of premature discontinuation of treatment in participants without disease progression according to RECIST v1.1 (e.g., unacceptable toxicity), efficacy assessments will continue to be performed until an EFS event has been determined or Month 60 post-randomization, whichever occurs first.

8.2.1. Radiological Assessment

For each participant, the same radiological method for head and neck and for chest must be used throughout the study. The schedule of collection of i.v. contrast-enhanced CT-scan or MRI of head and neck (which cover the orbits), CT-scan of the chest and ¹⁸F-FDG-PET scan (from the skull base to the proximal upper legs) is provided in Table 1-1 and Table 1-2.

¹⁸F-FDG-PET/CT-scan is preferred to facilitate pre-and post-treatment evaluation of metabolic response and the need for post-treatment neck dissection. If physical examination and imaging suggest residual disease at the primary site, a biopsy will be performed to confirm residual disease; otherwise, participants will undergo serial follow-up.

Additional imaging assessments may be performed at any time during the study at the Investigator's discretion to support the efficacy evaluations for a participant. Clinical progressive disease (PD) is recommended to be confirmed by imaging and/or endoscopy (i.e., biopsy).

If an off-schedule imaging assessment is performed because progression is suspected, subsequent assessments should be performed in accordance with the original imaging schedule.

Measurability of the tumor at baseline

At baseline, participants may be included with measurable disease or with only evaluable, non-measurable disease according to RECIST v1.1 and as assessed by the Investigator. Measurable disease is defined as the presence of at least one measurable nodal or non-nodal lesion. The assessment of participants at baseline according to RECIST v1.1 is covered in Appendix 13.5.

Non-measurable disease means that only non-measurable lesions exist at baseline. Guidance on how participants with only non-measurable disease at baseline will be evaluated for response and progression based on RECIST v1.1 is also defined in Appendix 13.5.

In this study, radiological response confirmation is not required either for partial or complete response.

For the purposes of the primary endpoint and to minimize bias, a BIRC will perform an independent assessment based on all efficacy imaging reading, review of selected clinical data and anatomopathological results.

Hence, all study imaging performed, including any off-schedule imaging performed, and anatomopathological assessments should be submitted to the designated imaging vendor for quality control and review by the BIRC, promptly after acquisition.

Such post-treatment consolidation neck dissections will encompass only the areas initially involved in the side of the neck in question (typically the involved area(s) and the adjacent immediate level). The extent of neck dissections performed for nodal recurrence, nodal progression, or salvage of disease at the primary will be determined by the treating surgeon.

Any treatment intervention in relation to the disease under study, including biopsies, END or surgery on the primary tumor as well as the anatomical site(s) and histopathology results must be reported in the eCRF.

If histopathology results or other clinical data are not consistent with the radiology report, then this information will be taken into account for the determination of tumor status according to the decision tree below (Figure 8-1).

8.3. Safety Assessments

Safety assessments will be performed according to the schedule in Table 1-1 and Table 1-3 and are further described below.

8.3.1. Physical Examination

The examination will include general appearance, sclera, cardiovascular system, pulmonary system, neurologic system, skin and gastrointestinal system. Abnormalities are to be recorded as medical history if started prior to the ICF signature or as an AE if started on or after ICF signature.

8.3.2. Vital Signs and ECOG Performance Status

Weight (to the nearest 0.1 kilogram or pound), height, ECOG performance score (see Appendix 13.1) and vital signs will be collected. Height will be measured at screening only.

Vital signs will include systolic/diastolic blood pressure (in sitting position after 10 minutes of supine rest), heart rate (after 10 minutes of supine rest), respiratory rate, and temperature.

8.3.3. Nutritional Status

Swallowing/nutritional status is to be done to determine if nasogastric tube, percutaneous endoscopic gastrostomy, or percutaneous endoscopic jejunostomy tube placement is needed.

An examination under anesthesia is recommended, including a direct laryngoscopy, bronchoscopy, esophagoscopy, and nasopharyngoscopy. At this point a biopsy can be taken if not yet readily available and if necessary.

A feeding tube is strongly recommended if the participant has swallowing disorders and / or weight loss. A feeding tube is mandatory if the participant has grade 3 dysphagia.

8.3.4. Dental Examination

A dental examination is to be performed by the site's dental clinic team according to institutional guidelines or by an external dentist (see Section 6.5.4.2.2).

8.3.5. Audiometry

An audiometry must be performed at screening. In addition, hearing clinical evaluation and audiometry should be performed at C2D1 and C3D1 if clinically indicated (except for France, see Appendix 13.6) and at any time if clinically indicated as per institutional or national guidelines. During the follow-up period, an audiometry is to be performed only if clinically indicated, as per institutional or national guidelines.

8.3.6. Electrocardiograms

A standard single 12-lead ECG will be recorded after 10 minutes of supine rest according to the schedule shown in Table 8-1.

Table 8-1 ECG collection plan

Study visit or cycle	Day	Time relevant to dosing
Screening	-28 to -1	n.a.
		Predose ^a
	1	0.5-2 hours postdose
Cycle 1		4-6 hours postdose
	8	Predose ^a
		0.5-2 hours postdose

n.a.: not applicable.

a To be performed prior to blood sampling.

If several ECGs (scheduled and unscheduled) are performed during the screening, the latest results should be recorded and used.

If ECGs are performed at the same time point as blood sampling (safety laboratory tests), ECG readings should be taken prior to sampling.

All ECG readings will be performed locally by the Investigator, or a cardiologist will be consulted if clinically indicated.

Additional ECGs can be performed if clinically indicated.

Abnormal ECG findings

In case of **abnormal** ECG findings (e.g., QTcF prolongation >30 ms compared to baseline, or QTcF interval >500 milliseconds, Torsade de pointes, ventricular tachycardia, ventricular fibrillation, flutter or any other new cardiac abnormality), triplicate ECG readings will be performed. If the abnormal ECG finding is confirmed after triplicate ECG readings, the participant should be referred to a local cardiologist.

Significant QTcF prolongation is defined as an interval >500 milliseconds (ms) or an interval which increases by 60 ms over baseline.

Management of participants with significant QTcF prolongation

If the QTcF prolongation is confirmed by **either** criterion (i.e., QTcF interval >500 ms **or** >60 ms increase from baseline) the following actions will be taken (see also Table 6-1):

- The treatment with xevinapant/matched placebo must be interrupted.
- The participant will be monitored including assessment of electrolytes in plasma (potassium calcium and magnesium), treated appropriately and closely followed (ECGs at least 3 times per week) until resolution to within 30 ms from baseline or QTcF <480ms.
- Stop any concomitant medication known to cause QTc prolongation.
- The participant will be referred to a cardiologist.
- The medical monitor will be consulted prior to administering further xevinapant/matched placebo doses.
- If the QTcF interval does not return to within 30 ms of baseline or <480 ms within 14 days, xevinapant/matched placebo must be permanently discontinued.
- For cisplatin/carboplatin, at the first occurrence, action taken for these agents is based on the Investigator's judgment. At the second occurrence, consider permanent discontinuation.

If the prolongation is confirmed by **both** criteria (i.e., QTcF interval > 500 ms **and** > 60 ms increase from baseline) the following actions will be taken:

- The treatment with xevinapant/matched placebo and cisplatin/carboplatin must be permanently discontinued.
- The participant will be monitored including assessment of electrolytes in plasma (potassium calcium and magnesium), treated appropriately and closely followed (ECGs at least 3 times per week) until resolution to within 30 ms to baseline.
- Stop any concomitant medication known to cause QTc prolongation.
- The participant will be referred to a local cardiologist.

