- 14. Active uncontrolled inflammatory disease (including rheumatoid arthritis, systemic lupus erythematosus, Sjögren syndrome, severe extensive psoriasis, and other autoimmune diseases) requiring ongoing treatment with anti-TNF medication.
- 15. Any concomitant medication known to prolong the QT interval that cannot be discontinued or replaced by safe alternative medication within 7 days prior to start of treatment.

- 16. Impaired cardiovascular function or clinically significant cardiovascular diseases, including any of the following:
 - Ongoing or history of uncontrolled or symptomatic ischemic myocardiopathy within 6 months prior to randomization.
 - Known left ventricular ejection fraction < 50%, left ventricular hypertrophy, ventricular arrhythmias, bradycardia (heart rate < 50 bpm).
 - History of myocardial infarction, or severe/unstable angina, within 6 months prior to randomization.
 - New York Heart Association grade ≥ 3 congestive heart failure.
 - Congenital long QT syndrome.
 - Family history of long QT syndrome.
 - Symptomatic pulmonary embolism within 6 months prior to randomization.
 - Ongoing or known history of transient ischemic attacks or stroke within 6 months prior to randomization.
 - QTc using Fridericia's formula (QTcF) interval > 450 ms for males and > 470 ms for females.
- 17. Symptomatic pulmonary disease requiring continuous or intermittent oxygen supply.
- 18. History of another malignancy within the last 3 years prior to randomization, with the exception of completely resected non-melanoma cell skin cancer outside the head and neck area or completely resected stage I breast cancer, or completely resected in-situ non-muscular invasive bladder, cervix and/or uterine carcinomas or T1a squamous cell carcinoma of the esophagus.
- 19. Known contraindication to undergoing positron emission tomography with 2-deoxy-2-[fluorine-18] fluoro-D-glucose (18F-FDG-PET) scans, and/or both contrast-enhanced MRI and contrast-enhanced CT scans.
- 20. Known allergy to xevinapant, cisplatin, carboplatin, other platinum-based agent or any excipient known to be present in any of these products or in the placebo formulation.
- 21. Non-compensated or symptomatic liver cirrhosis (Child-Pugh score: B or C).

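### For a participant with baseline QTcF below 420 ms, a value above baseline + 60 ms but below 480 ms is both an interruption trigger and already resolved, so the follow-up and 14-day rules in Protocol 8.3.6 have no effect in that band

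*Protocol*

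**What the plan says.** Protocol Section 8.3.6 sets the trigger: "Significant QTcF prolongation is defined as an interval >500 milliseconds (ms) or an interval which increases by 60 ms over baseline". The line that opens the list of actions words the change criterion slightly differently, as ">60 ms increase from baseline) the following actions will be taken".

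If either criterion is confirmed, "The treatment with xevinapant/matched placebo must be interrupted". Electrolytes are checked, QT-prolonging co-medication is stopped, a cardiologist sees the participant, and the medical monitor is consulted before any further dose. ECGs are repeated at least three times a week "until resolution to within 30 ms from baseline or QTcF <480ms". Permanent discontinuation follows "If the QTcF interval does not return to within 30 ms of baseline or <480 ms within 14 days".

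If both criteria are met, xevinapant or placebo and the platinum agent are stopped for good. ECG follow-up then runs "until resolution to within 30 ms to baseline", with no 480 ms alternative.

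Protocol Section 5.2, exclusion 16, excludes "QTc using Fridericia's formula (QTcF) interval > 450 ms for males and > 470 ms for females". It sets no lower limit, so baselines below 420 ms are eligible. Section 8.3.6 also refers to Table 6-1, whose body is not in the text available for this review.

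**The concern.** The trigger has a change-from-baseline arm, but the resolution test can be met on the absolute value alone. A participant who enters through the change arm can therefore satisfy the exit test on the same tracing, or later while the rise is still large enough to be called significant.

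Two safeguards depend on that exit test: how long the intensified ECG follow-up lasts, and whether the 14-day rule ends treatment. Scheduled ECGs (Table 8-1) occur only at screening and on Days 1 and 8 of Cycle 1, while dosing runs for six cycles. After Day 8 of Cycle 1, the repeat ECGs in this section are the only ones that Section 8.3.6 mandates; others are done if clinically indicated. If that series can end as soon as it starts, a persistent rise of more than 60 ms may not be followed.

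**Working it through.** The plan states no figure to reproduce, so the check applies the rules to QTcF values directly. Let B be the baseline and Q the on-treatment QTcF, in ms.

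**Inputs**
- Trigger (8.3.6): Q > 500 or Q − B > 60.
- Both-criteria branch (8.3.6): Q > 500 and Q − B > 60.
- Resolution and 14-day test, either-criterion branch (8.3.6): Q − B ≤ 30 or Q < 480.
- Eligible baseline (5.2, exclusion 16): up to 450 for males and 470 for females, with no lower limit.

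**Step 1: where trigger and resolution coincide.** A rise above 60 cannot also be within 30, so overlap through the change arm needs Q > B + 60 and Q < 480. Such values exist only if B + 60 < 480, that is, B < 420. Example: B = 400, Q = 465. The rise is 465 − 400 = 65, which exceeds 60, and 465 < 480.

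**Step 2: which arm these participants enter by.** If B < 440 and Q > 500, then Q − B > 60, so the both-criteria branch applies. Anyone with B < 420 therefore reaches the either-criterion branch only through the change arm.

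**Step 3: results by baseline**

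| B | Triggered and already resolved | Triggered, not resolved (14-day rule runs) | Rise still counted as resolved under the 480 ms test |
|---|---|---|---|
| 360 | above 420, below 480 | 480 to 500 | up to just under 120 |
| 380 | above 440, below 480 | 480 to 500 | up to just under 100 |
| 400 | above 460, below 480 | 480 to 500 | up to just under 80 |
| 410 | above 470, below 480 | 480 to 500 | up to just under 70 |
| 420 | none | above 480, to 500 | up to just under 60 |

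The last column is 480 − B. A search on a 0.5 ms grid gave the same pattern, with no overlap at 420 or above.

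**Step 4: resolving while still significant.** Take B = 400 and a first value of 490. The rise is 90, Q is not below 480, and the 14-day period starts. At Q = 479 the event counts as resolved, yet the rise is 479 − 400 = 79, still above the 60 ms trigger.

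**Step 5: sensitivity to reading.** Whether the trigger is a rise of 60 or of more than 60, the limit stays at B < 420, because at B = 420 a rise of 60 gives exactly 480, which is not below 480. If both resolution conditions were required instead of one, the overlap would be empty at every baseline. This shows that the result turns on how one conjunction is read; it is not a proposal.

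**The case against.** The strongest reply is that much of the rule works. A reader might infer that the interruption does not operate, or that a rise of more than 60 ms has no consequence when baseline is below 420 ms. The text does not support either. Interruption is mandatory on a confirmed trigger whatever the 480 ms status, and the electrolyte checks, referral, co-medication and medical-monitor steps do not depend on it. The 14-day rule runs at 480 to 500 ms, and above 500 ms these participants stop permanently. All of this stands and limits the point to the end condition.

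The medical-monitor consultation is a real safeguard at every site. It does not supply the missing condition, because Section 8.3.6 gives the monitor no QTcF criterion other than the resolution test in question.

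Table 6-1 may contain a clear resumption rule. That cannot be checked here. If it does, Section 8.3.6 would still need to agree with it.

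The different resolution test in the both-criteria branch might be read as a further contradiction. It is explainable: treatment has already stopped there, so the test only ends ECG follow-up. Near the upper eligibility limits, trigger and resolution lie close together, but no value meets both, so that is a narrow margin and not a conflict.

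Finally, SAP Section 15.5.1 tabulates QTcF changes above 60 ms from the ECG data, independently of this clause. That is correct, but its summary tables use scheduled visits only; follow-up ECGs at unscheduled times appear in the listing, if they are done.

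**Conclusion.** The point holds for a defined band. For baselines below 420 ms, any QTcF above baseline + 60 ms and below 480 ms meets trigger and resolution together. In that band the close ECG follow-up has no duration and the 14-day rule cannot take effect unless QTcF later reaches 480 ms. A participant who starts at 480 to 500 ms can resolve with a rise still above 60 ms. This is a stated safety rule that defeats its own end condition when followed as written.

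The conclusion assumes the ordinary reading of the resolution clause, in which meeting either alternative is enough, and that Table 6-1 does not override it. A reader might go on to infer that a large share of participants is affected. The documents do not support a figure: they give no baseline QTcF distribution and no rate of confirmed rises above 60 ms, and a low baseline alone does not put anyone in the band.

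**What to change.** In Section 8.3.6, reconcile the definition of significant prolongation (including a rise of 60 ms versus more than 60 ms), the resolution test in the either-criterion branch and the 14-day rule. Check all three against the Table 6-1 row that the section cites. The revised text should ensure that no QTcF value meets trigger and resolution at once, and should say which resolution test applies to the absolute trigger and which to the change trigger. The choice of thresholds belongs to the sponsor's safety team.

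The cost is a wording change in the next amendment, with a matching edit to Table 6-1 if it differs. The rewording itself adds no scheduled ECGs and no new data items.
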